## 12.6 Sample Size

### 12.6.1 Accrual estimates

Target enrollment was approximately 30 participants per month with 6-10 per site. As of March 31, 2022 and with 34 months of enrollment, we have enrolled 381 participants. Enrollment slowed due to the COVID-19 pandemic. We have been in close communication with PCORI who were supportive of our continuing enrollment, as safe and feasible, through the pandemic until we met our target enrollment goals. PCORI has been supportive of the extended timeline to enroll patients.

### 12.6.2 Sample size justification

It is hypothesized that surgeon-palliative care co-management (intervention) perioperative palliative care will improve patient postsurgical quality of life as compared to surgeon-alone management of care (control). Thus, the null hypothesis is that the intervention and control groups will not differ in postsurgical quality of life measures.

The estimated sample size is 186 patients per arm or 372 patients total (380 patients was our goal). The sample size and power of this study was based on the primary outcome quality of life measure, FACIT-Pal. With this sample size, using an unpaired two-sample t-test, the present study is powered to detect an anticipated small-to-moderate effect size of 0.4 at 12 weeks with 90% power and probability type I error of 0.05 (two-sided). This power analysis includes a 86% participant completion rate as well as a variance inflation factor of 20%.

One of the study sites had a study coordinator abruptly quit the position in 2019 and consequently data on 20 participants from that site were compromised. Following the same methodological approach described in the published protocol paper (which anticipated a LTFU rate of 14%), we performed a re-estimate of the required sample size for this study in December 2020 and discovered that it was higher than anticipated (28%) due to the study coordinator turnover and interruptions caused by the pandemic. This was discussed with the funder (PCORI); the study team and PCORI had consequently agreed to target 420 enrollees to ensure sufficient sample size and study power. However, in December 2021, we re-evaluated our LTFU rate and found that it had markedly improved during the most recent year of enrollment and was now the same as was originally anticipated. In communication with PCORI, we returned the enrollment rate to 380.

### **12.6.3 Effect size justification**

The means, standard deviations, and effect sizes were based on previous research  supporting that patients receiving medical oncologist-palliative care co-management had better quality of life (measured by Functional Assessment of Cancer Therapy – Lung; FACT-L) than patients receiving medical oncologist alone management. Mean score differences in FACT-L were  $98.0 \pm 16.7$  ( $n = 74$ ) in the intervention group and  $91.5 \pm 16.5$  ( $n = 77$ ) in the control group resulting in an effect size of 0.42 (unpaired two-sample t-test). Since the FACIT-Pal scale used in this study is a direct corollary of the FACT-L scale, this effect size was used to estimate the sample size for the present study. The sample size and power of this study are based on the quality of life measure, FACIT-Pal. Based on the unpaired two-sample t-test, the present study was powered to detect an anticipated small-to-moderate effect size of 0.4 at 12 weeks with 90% power and probability type I error of 0.05 (two-sided). Patients will be nested within the four intervention sites, which will introduce some within-site correlation that could decrease the efficiency of these estimators. Thus, a variance inflation factor of 20% was incorporated in the sample size estimation. Additionally, it is predicted that this study will have missing data due to patients discontinuing participation in the study and death. Based both on the research team's past experiences conducting studies in this population and already published perioperative mortality data, we assumed a dropout rate of 11% and a mortality rate at 12 weeks of 3%; thus, patient completion rate was estimated to be 0.86. Together, with the assumptions outlined here, the estimated sample size needed for the present study is a total of 186 patients per arm (372 patients total) and our goal was to recruit 380 patients.

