### 11.2 Protocol Review and Amendments

The protocol, the proposed informed consent and all forms of participant information related to the study (e.g. advertisements used to recruit participants) will be reviewed and approved by the Stanford IRB and Stanford Cancer Institute Scientific Review Committee (SRC). Any changes made to the protocol will be submitted as a modification and will be approved by the IRB prior to implementation. The Protocol Director will disseminate the protocol amendment to all participating investigators. Investigators will be expected to obtain IRB approval within 90 days for all amendments.

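### Section 12.6.3: the printed means and SDs give an effect size of 0.39, not 0.42, and the sample size of 372 was computed from 0.40, not from the value said to be used

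*Combined protocol and SAP*

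**What the plan says.** Section 12.6.3 bases the effect size on a published trial of palliative care in medical oncology. It prints the FACT-L results as 98.0 ± 16.7 (n = 74) with the intervention and 91.5 ± 16.5 (n = 77) in the control group, "resulting in an effect size of 0.42 (unpaired two-sample t-test"). It argues that FACIT-Pal corresponds directly to FACT-L and concludes that "this effect size was used to estimate the sample size for the present study". Shortly afterwards the same section says that "the present study was powered to detect an anticipated small-to-moderate effect size of 0.4 at 12 weeks with 90% power", at a two-sided type I error of 0.05. Section 12.6.2 adds: "This power analysis includes a 86% participant completion rate as well as a variance inflation factor of 20" percent. Both sections arrive at 186 per arm, 372 in total, with a recruitment goal of 380.

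Section 12.6.2 also gives the history of the target. After a coordinator left one site in 2019, "data on 20 participants from that site were compromised". In December 2020 the team re-examined loss to follow-up and "discovered that it was higher than anticipated (28%) due to the study coordinator turnover and interruptions caused by the pandemic"; the target rose to 420. In December 2021 it re-evaluated the rate and "found that it had markedly improved during the most recent year of enrollment and was now the same as was originally anticipated"; the target went back to 380.

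The synopsis and section 1.1 give 380. The tables in 10.1.2 and 10.2.2 give 420.

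**The concern.** The effect size is the one input to the sample size that rests on outside data, and 12.6.3 prints everything needed to check it. The stated result does not follow from the printed figures. The sentence saying which value entered the calculation then conflicts with the sample size that came out. A reader who tries to reproduce the derivation fails twice.

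At stake is whether the stated 90% power rests on the evidence quoted for it. If the printed means and SDs are right, the planning value of 0.40 lies slightly above the cited effect, not below it.

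Two smaller matters belong to the same sections. The current text gives two different sample sizes. And the return from 420 to 380 depends on a loss rate whose denominator is not stated.

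**Working it through.** **Inputs.** From 12.6.3: means 98.0 and 91.5, SDs 16.7 and 16.5, n = 74 and 77, stated effect size 0.42, planning value 0.4, and dropout of 11% plus mortality of 3%, so completion 0.86. From 12.6.2 and 12.6.3: 90% power, two-sided 0.05, unpaired t-test, variance inflation 20%. Power is computed with the noncentral t distribution.

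**1. The plan's own sample size.** At d = 0.40 the t-test needs 132.3, rounded up to 133 per arm. Then 133 × 1.20 = 159.6, and 159.6 / 0.86 = 185.6, rounded up to 186 per arm, or 372. This matches the plan exactly.

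**2. Effect size from the printed data.**
- Pooled SD = √[(73 × 16.7² + 76 × 16.5²) / 149] = 16.598.
- d = (98.0 − 91.5) / 16.598 = 6.5 / 16.598 = 0.3916.
- Rounding limits: 6.4 / 16.648 = 0.384 and 6.6 / 16.548 = 0.399.
- Dividing by one arm's SD instead gives 6.5 / 16.5 = 0.394 or 6.5 / 16.7 = 0.389.
- A value of 0.42 would need an SD of 6.5 / 0.42 = 15.5, which neither arm has.

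**3. Sample size by effect size, same formula.**

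| d | n per arm (t-test) | × 1.20 / 0.86 | Per arm | Total |
|---|---|---|---|---|
| 0.42 (stated) | 120.1 → 121 | 168.8 | 169 | 338 |
| 0.40 (planning value) | 132.3 → 133 | 185.6 | 186 | 372 |
| 0.3916 (printed data) | 138.0 → 139 | 194.0 | 194 | 388 |

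Of the three, only 0.40 gives 372.

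**4. Power at the planned 14% loss.** Effective n per arm = (N / 2) × 0.86 / 1.20, which is 133.3 at 372 and 136.2 at 380.

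| d | N = 372 | N = 380 |
|---|---|---|
| 0.40 | 90.2% | 90.8% |
| 0.3916 | 89.0% | 89.6% |

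**5. Loss that 380 can bear at 90% power.**
- At d = 0.40, completers needed are 2 × 133 × 1.20 = 319.2, so the maximum loss is 1 − 319.2 / 380 = 16.0% (16.4% with the unrounded 132.3).
- At d = 0.3916, completers needed are 2 × 139 × 1.20 = 333.6, so the maximum loss is 12.2% (12.8% unrounded).

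These limits apply to loss over all enrolled patients. Section 12.6.2 gives no cumulative completion count to set beside them.

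**The case against.** The strongest reply is that nothing operative is wrong. Both 12.6.2 and 12.6.3 state that the trial is powered for 0.4, the 372 follows exactly from that, and both 0.42 and 0.39 round to 0.4. This stands as far as the sample size goes. It does not rescue the 0.42, which the printed figures cannot give, or the sentence saying that this value was used, since it would have led to 338.

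A reader might infer that 0.40 was offered as a cautious step down from 0.42. The text does not say so; it calls 0.4 small to moderate and does not describe it as conservative.

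A reader might also infer from the loss history that 380 patients cannot give 90% power. The documents do not support that. The December 2021 sentence can be read as an overall rate equal to the planned 14%, in which case power at 0.40 is 90.8%. It can also be read as the rate in the latest year only, and the text does not settle which. Adding the 20 compromised participants to a 14% loss is not safe either. The 28% is attributed partly to the same coordinator turnover, so they may already be counted. No split of enrolment by period is given, so a mixture of early and late loss rates would be guesswork. Finally, the power sentence is a planning statement with its own completion assumption, and 12.6.1 reports 381 patients already enrolled, so restating power changes no decision on recruitment.

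**Conclusion.** The arithmetic error is certain and minor. The printed means and SDs give 0.39, the stated 0.42 cannot result from them, and 0.42 was not the value used. The 372 is correct for 0.40. If the printed data stand, power at the cited effect is 89.0% at 372 and 89.6% at 380, slightly under the stated 90%. Those figures assume the plan's 14% loss, its 20% inflation and its complete-case t-test; the mixed model in 12.4.2 can use partial data and may do somewhat better. The documents cannot show whether the 0.42 or the quoted means and SDs are misreported.

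The 420 in the tables of 10.1.2 and 10.2.2 is a plain inconsistency with the synopsis, 1.1 and 12.6.

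The loss rate is a request for clarification only. The 90% statement at 380 holds at d = 0.40 if cumulative loss is about 16% or less (about 12% to 13% at d = 0.39). The plan does not report whether that condition is met.

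**What to change.** - **12.6.3:** check 0.42 against the cited source and correct either it or the quoted means and SDs. Replace the sentence on which effect size was used with a statement that 0.40 was the planning value. If the means and SDs stand, give 0.39 and add that power at that value is about 89% to 90%.
- **10.1.2 and 10.2.2:** change 420 to 380 patients in both tables.
- **12.6.2:** say whether the December 2021 loss rate is cumulative over all enrolled patients and whether it counts the 20 compromised participants. If it is 14% cumulative, one sentence is enough. If cumulative loss exceeds about 16%, restate the power at 380.

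The cost is one check of the source, one completion count pooled over arms (which reveals no allocation) and a few lines of wording. Under 11.2, "Any changes made to the protocol will be submitted as a modification and will be approved by the IRB prior to implementation", so this is best combined with the next amendment. Design, enrolment and analysis do not change.

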### **3.5 Randomization Procedures**

Randomization is immediately after enrollment, stratified by study site, and completed via computer-generated random allocation with a block size of 6 by using the REDcap database. Understandably, neither the patient, caregiver, nor surgeon can be blinded to intervention allocation. However, the principal investigator (PI) and analysis team are blinded to participant randomization and the research team acquiring outcome data, whenever possible, is blinded to participant randomization.

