### 12.4.2. Analysis Plan

The effect of group assignment (intervention or control) on the quality of life will be tested. Differences in outcomes between two arms at each visit will be tested by the two-sample t-test/Mann-Whitney test or Fisher's exact test/chi-squared test based on the data types of the outcomes. The effect of intervention on the quality of life after accounting for various confounding variable will be determined using a linear mixed model that accounts for within-subject variations due to repeated measures. Sensitivity analyses will assess whether there are differential effects on contingent on patient or study site characteristics on the primary outcomes.

The overall level of statistical significance was set at  $p<0.05$ . For all models, the research team will identify possible confounding variables for model adjustment, including baseline attributes. Using peer-reviewed literature, the research team has identified confounding variables that models will be adjusted for. These covariates include patient gender, age, race, education, and health status.

Qualitative data related to secondary outcomes will be transcribed, de-identified, and analyzed

based on qualitative description. A HIPPA-compatible, professional transcription service will be used for interview transcription. NVivo software will be used for qualitative analyses. A codebook will be determined by a three-person team with a single coder then analyzing the transcripts. Line-by-line, axial, and theoretical consensus coding will be used to organize and summarize findings, which will be validated through triangulation, member checking, and search for disconfirming data.

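### Randomisation is stratified by site, but no planned test or model names site as a term, and the reason given for the 20% variance inflation does not fit a comparison balanced within sites

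*Combined protocol and SAP*

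**What the plan says.** Section 3.5 states: "Randomization is immediately after enrollment, stratified by study site", with computer-generated allocation in blocks of 6. Section 12.1.1 repeats this. The unit of randomisation is the individual participant.

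Section 12.6.3 sizes the trial as follows: "Based on the unpaired two-sample t-test", for an "effect size of 0.4 at 12 weeks with 90% power" and a two-sided 5% level. It says that nesting of patients in four sites causes correlation "which will introduce some within-site correlation that could decrease the efficiency of these estimators", and adds a variance inflation factor of 20% for this. No intraclass correlation or derivation is given. With a completion rate of 0.86, the result is 186 per arm (372 in total), and the recruitment goal is 380.

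Section 12.4.2 plans a two-sample t-test or Mann-Whitney test at each visit and "a linear mixed model that accounts for within-subject variations due to repeated measures". The covariates it names are gender, age, race, education and health status. Section 12.5.2 uses the same approach for secondary outcomes and adds Kaplan-Meier or Cox methods for some of them. In the analysis plans, site is mentioned only in 12.4.2, in a sensitivity analysis of whether effects differ by patient or site characteristics.

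**The concern.** The two parts of the plan do not fit together. The sample size section treats correlation within site as important enough to add 20% to the variance, but the analysis sections name site in no test or model.

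The direction of the adjustment is also doubtful. Correlation within sites inflates the variance of a treatment comparison when whole sites receive one arm. Here both arms are present in near-equal numbers at every site, so a difference shared by all patients at a site drops out of the comparison. Site differences then do harm only if they stay in the residual variance. The standard error is then estimated too large, and the precision that stratification offers is not collected.

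At stake are a test that runs below its nominal level, a small loss of power, and a power statement that rests on a reason that does not apply.

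**Working it through.** **1. Reproduce the plan's figure.** Inputs from 12.6.3: effect 0.4 SD, two-sided 0.05, power 90%, inflation 1.2, completion 0.86.

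- Two-sample t-test: 132.3, rounded up to 133 per arm.
- 133 × 1.2 = 159.6; 159.6 / 0.86 = 185.6, rounded up to 186 per arm.

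The stated 186 is reproduced. With 186 × 0.86 = 160 evaluable per arm and the factor of 1.2, power is 90.2%.

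**2. Remove the factor and keep everything else.**

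- 133 / 0.86 = 154.7, so 155 per arm (310 in total), against 186 (372): 31 fewer per arm, 62 in total.
- 186 per arm: 160 evaluable, power 94.6%.
- 190 per arm: 190 × 0.86 = 163.4 evaluable, power 95.0%.

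**3. Effect of leaving site out.** Let r be the share of outcome variance that lies between sites. The documents do not give r, so 0.01 to 0.10 is an assumption. Total SD is set to 1, with n = 160 evaluable per arm. With arms balanced within site:

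- true variance of the difference: 2(1 − r)/n
- variance that the unadjusted t-test estimates: about 2/n, too large by a factor 1/(1 − r)
- type I error of the t-test: about 2[1 − Φ(t / √(1 − r))], where t = 1.967 on 318 degrees of freedom
- power of the t-test: about 1 − Φ[(t√(2/n) − 0.4) / √(2(1 − r)/n)]
- power with site in the model: that of a t-test at effect 0.4/√(1 − r)

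| r (assumed) | Type I error, site ignored | Power, site ignored | Power, site in model | Difference |
|---|---|---|---|---|
| 0.01 | 4.8% | 94.7% | 94.8% | about 0.1 point |
| 0.05 | 4.35% | 95.1% | 95.5% | about 0.5 point |
| 0.10 | 3.8% | 95.5% | 96.4% | about 0.9 point |

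The formula uses a normal approximation and gives 4.9% at r = 0, so it overstates the conservatism by about 0.1 point.

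**4. Simulation check.** Four sites of 80, blocks of 6, 4,000 runs per setting. The Monte Carlo standard error near 5% is √(0.05 × 0.95 / 4,000) = 0.34 points. At r = 0.10, type I error was 3.7% without site and 4.9% with it; power was 95.0% and 96.0%. At r = 0.05, type I error was 4.4% and 5.0%. The simulation agrees with the formulas.

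**5. Could another reason give 1.2?** Suppose treatment effects vary between sites with SD s, and the four sites, of equal size, are treated as a random sample. This adds s²/4 to the variance of the difference. Setting s²/4 = 0.2 × 2/160 = 0.0025 gives s = 0.10 outcome SD. The factor could be defended on this ground, but the documents do not state it.

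**The case against.** **The power figure is not wrong.** A reader might infer that the 90% is an error or that the trial is underpowered. The documents do not support that. The figure follows from disclosed inputs, and the factor pushes it in the safe direction. This part of the objection stands in full.

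**Site is not excluded.** A reader might infer that the plan rules out adjusting for site. It does not. The covariate list in 12.4.2 and 12.5.2 is introduced as a list of inclusions, and the team may identify further variables. The accurate statement is that site is not named. Still, an open list leaves the choice to the analyst, whereas a stratification factor is known from the start and can be fixed in advance.

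**Type I error is not inflated.** Ignoring a stratification factor might suggest false positives. With individual randomisation balanced within site, the error goes the other way.

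**Site inflation is not confined to cluster trials.** As step 5 shows, variation in the treatment effect between sites can raise the variance in an individually randomised trial. With a specialist team delivering care at four sites, such variation is plausible. This supports keeping a margin, but not the reason given, which is correlation from nesting.

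**The loss is small.** Over the assumed range it is about one power point or less, and the between-site shares are not from the documents. This also stands and sets the weight of the point.

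**Conclusion.** The point holds as a low-cost improvement to the analysis and a correction to one stated reason. It does not threaten the trial's validity.

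Site, the stratification factor, should be a pre-specified term and at present is not. For an assumed between-site share up to 0.10, ignoring it puts the t-test at between about 4.8% and 3.8% instead of 5%, and costs at most about 0.9 points of power. The 20% inflation is not justified by within-site correlation. The 186 per arm is nevertheless correct on the plan's inputs and conservative on its other assumptions.

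These results assume four sites of similar size, near-equal arms within each site after losses, 86% completion and an effect of 0.4 SD. The figures are for the t-test at a single visit. In a mixed model without site, site differences would fall into the between-patient variance, so the direction is the same, but the size was not calculated and the other covariates may absorb part of it.

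The 62 patients in step 2 should not be read as a reason to alter recruitment. Section 12.6.1 reports 381 enrolled by 31 March 2022.

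**What to change.** 1. In 12.4.2 and 12.5.2, add study site as a fixed effect to the models, alongside the covariates already named.
2. In 12.4.2, state that the primary inference on quality of life at three months comes from the site-adjusted model, with the unadjusted tests at each visit as supporting results.
3. In 12.6.3, choose one of two wordings. Either drop the 1.2 and restate power as about 94.6% at 372 and 95.0% at 380, or keep the 1.2 and describe it as a margin for treatment effects that differ between sites, with the assumed size of that variation.

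The cost is a few sentences and three degrees of freedom for four sites, out of about 318 in the comparison at three months. No extra data are needed, and enrolment does not change.

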### **12.7 Criteria for future studies**

This is a randomized controlled superiority trial that is powered to detect a difference in the primary outcome, quality of life as measured by FACIT-PAL. It is neither a pilot study nor a part of a sequence of trials.

